6.3.5 Abnormal Physical Examination Findings

Clinically significant changes, in the judgement of the Investigator, in physical examination findings (abnormalities) will be recorded as adverse events.

6.3.6 Other investigation abnormal findings

In addition, abnormal objective test findings that result in a change in study drug dosage or administration schedule, or in discontinuation of the drug, or require intervention or diagnostic evaluation to assess the risk to the patient, should be recorded as adverse events.

6.3.7 Recording and Follow-up of Adverse Events

At each visit the patient should be asked a non-leading question such as: "Do you feel different in any way since starting the new treatment/the last assessment?"

All observed or volunteered adverse events, regardless of treatment group or suspected causal relationship to study drug, will be recorded on the adverse event page(s) of the CRF using the standard UHB reporting forms. Adverse events already recorded and designated as 'continuing' should be reviewed at each subsequent assessment.

For all adverse events, the Investigator must pursue and obtain information adequate both to determine the outcome of the adverse event and to assess whether it meets the criteria for classification as a serious adverse event requiring immediate notification to the Sponsor. For all adverse events, sufficient information should be obtained by the Investigator to determine the causality of the adverse event (i.e., study drug or other illness). The Investigator is required to assess causality and record that assessment on the CRF. Follow-up of the adverse event, after the date of therapy discontinuation, is required if the adverse event or its sequelae persist. Follow-up is required until the event or its sequelae resolve or stabilise at a level acceptable to the Investigator and the Sponsor's clinical monitor or his/her designated representative.

Annual safety reports will be sent to the Sponsor, the main REC and the MHRA.

6.4 Serious Adverse Events

6.4.1 Definitions

All serious adverse events (as defined below) regardless of any suspected relationship to the study drug must be reported immediately to the sponsor. If the immediate report is submitted by telephone, this must be followed by detailed written reports using the SAE report form.

A serious adverse event is any adverse event occurring at any dose that:

- 1. results in death;
- 2. is life threatening.(that is any event that places the patient at immediate risk of death from the reaction as it occurred. It does not include a reaction that, had it occurred in a more severe form, might have caused death)
- 3. results in in-patient hospitalisation or prolongation of existing hospitalisation, excluding admission for social or administrative reasons
- 4. results in a persistent or significant disability or incapacity, where disability is a substantial disruption of a person's ability to conduct normal life functions;
- 5. results in congenital anomaly or birth defect in the offspring of a patient who received the study drug;

Initial hospitalisation is defined as any in-patient admission (even if less than 24 hours). For chronic or long-term in-patients, in-patient admission also includes transfer within the hospital to an acute/intensive care in-patient unit.

Prolongation of hospitalisation is defined as any extension of an in-patient hospitalisation beyond the stay anticipated/required in relation to the original reason for the initial admission, as determined by the Investigator or treating physician. Prolongation in the absence of a precipitating, treatment-emergent, clinical adverse event (i.e. not associated with the development of a new adverse event or worsening of a pre-existing condition) may meet criteria for "seriousness" but is not an adverse experience and thus is not subject to immediate reporting to the Sponsor. Pre-planned treatments or surgical procedures should be noted in the Screening documentation for the entire protocol and/or for the individual patient. Hospitalisation for a procedure related to the disease under investigation (e.g. puncture of effusion), is not to be considered as a serious adverse event.

6.4.2 Reporting Requirements

Within 24 hours of a member of the research team becoming aware of a serious adverse event the Sponsor must be notified. The Investigator (or delegated person) will make an initial report, orally or in writing. Oral reports will be followed up in writing within 24 hours of the initial report. Written reports will be made by completing the UHB SAE/SUSAR reporting form. (Appendix 4). The initial report will include as much information as is available at the time.

Investigators (or delegated persons) will provide follow-up information, each time new information is available, using the UHB Research Related SAE/SUSAR Follow-up Report form (Appendix 4), until the SAE has resolved or a decision for no further follow up has been taken.

The Chief Investigator will provide the main REC with copies of all reports and recommendations of any independent Data Safety Monitoring Board established for a trial. A written acknowledgement is required from the main REC to confirm that they have received this notification.

6.4.3 Mandatory Information for Reporting an SAE

The following information is the minimum that must be provided to the sponsor pharmacovigilance contact within 24 hours for each SAE:

- Trial number
- Centre number
- Patient number
- Adverse event
- Seriousness criteria with immediate outcome
- Investigator's name and contact details

The additional information included in the SAE form must be provided to the sponsor or representative as soon as it is available. Upon receipt of the initial report, the sponsor will ask for the Investigator's causality assessment if it was not provided with the initial report.

The Investigator is encouraged to report a diagnosis or a syndrome rather than individual signs or symptoms. The Investigator should also try to separate a primary adverse event considered as the foremost untoward medical occurrence from secondary adverse events which occurred as complications.

6.4.4 Follow-up of Serious Adverse Events

Serious adverse events, especially those for which the relationship to drug is different from "not related" should be followed up until they have returned to Baseline status or stabilised at a level acceptable to the Investigator and the Sponsor's clinical monitor or his/her designated representative.

If a clear explanation is established for the relationship assessment it should be recorded on the CRF.

6.5 Deaths

All deaths occurring during the study, or within 28 days after the last dose of study drug, must be reported as a SAE within 24 hours. However, deaths due unequivocally to progression of disease are not to be considered as SAEs.

7. INFORMED CONSENT

7.1 Informed Consent

The Investigator, or a person designated by the Investigator, will explain the benefits and risks of participation in the study to each patient and obtain written informed consent.

Written informed consent will be obtained prior to the patient entering the study (before initiation of any study-related assessment or procedure and before administration of study drug). The final, version dated, form must be approved by the REC. Each patient's original consent form, personally signed and dated by the subject and by the person who conducted the informed consent discussion, will be filed in the patients medical notes. The Investigator will supply all enrolled patients with a copy of their signed informed consent and the patient information sheet. A copy of the signed consent form will be kept in the study site file.

The consent form may need to be revised during the trial should important new information become available that may be relevant to the safety of the patient. In this instance approval should always be given by the REC and existing patients informed of the changes. This is documented in the same way as previously described.

With the consent of the patient the patient's GP will be notified of their participation in the trial.

8. STATISTICAL CONSIDERATIONS

8.1 Subject Classification and Definitions

• Enrolled subject:	Subject fully informed about the study who has given written informed consent to participate (before any occurrence of trial related procedure)
• Screened failure subject:	Enrolled subject who fails to fulfil one or more entry criteria and thus does not proceed to the treatment phase of the study. Although not exposed to study medication, they may have been exposed to some study related procedures. Records up to the time of premature termination should be completed including the reason for termination
• Treated subject :	Enrolled subject who is treated with at least one dose of study medication
• Treatment Completed subject:	Treated subject who has completed all specified phases/assessments of the active treatment.
• Study Completed subject:	Treated subject who has completed all specified phases/assessments of the study.
• Drop-out:	Treated subject who did not complete the study and or treatment

8.2 Analyses Populations Definitions

•	Screened population:	All subjects enrolled
•	Safety population:	All subjects who received at least one injection of study medication .
•	Intention-to-treat (ITT) population:	All treated subjects
•	Per protocol (PP) population:	All subjects in the ITT population for whom no major protocol violations / deviations occurred

8.2.1 Populations Analysed

The primary analysis based on the primary efficacy endpoint(s) will be performed on the ITT population. In addition, a secondary analysis will be performed using the PP population.

All secondary analyses will be carried out using the ITT population.

The analyses of safety data will be performed based on the Safety population.

The rules for the allocation of subjects to each of the analysis populations will be defined and documented during a data review meeting held prior to database lock. During the data review meeting, based on minor or major protocol violations / deviations, subjects may be excluded from the ITT/PP populations.

8.3 Sample Size Determination

The trial will test the null hypothesis (H0) that the proportion of responders (defined as a subject who achieve STTCL (< 50 ng/dL) 4 months after the first injection is lower or equal to 80% against the alternative hypothesis H1 that the proportion of responders is larger or equal to 95%.

Considering the method developed by A'Hern for exact calculation in single-stage phase II designs, a sample of 42 subjects with a cut-off value fixed at 39 subjects allows the rejection of the null hypothesis with an alpha-risk of 2% (one sided) and an 84% power. A drop out rate of up to 10% is anticipated and to accommodate withdrawals the study sample size has been increased to no more than 50 subjects in total.

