	24 hours after the injection, the site will call the patient to check whether there have been any tolerability issues following the injection. Details will be recorded in the patients CRF.
	Patients will return to the clinic for a follow up assessment 2 months after the Baseline visit (visit 4). At this visit any new or altered adverse events or concomitant medications will be recorded. Blood samples will be collected (for analysis of levels of STT, PSA and plasma triptorelin).
	Four months after the Baseline visit, patients will return for an End of Study Visit (Visit 5) a physical examination will be performed and vital signs (weight, blood pressure, pulse rate) will be recorded. Blood samples will be collected (for analysis of levels of STT, PSA, plasma triptorelin, haematology and biochemistry). A dipstick urinalysis will be performed. Details of any new or altered adverse events or concomitant medications will be recorded.
	At the end of their study participation, patients will receive the standard medical care for their prostate cancer. This may involve treatment with Decapeptyl SR or any other marketed LHRHa at the discretion of the treating physician.
Study Population:	Approximately 50 patients will be enrolled in order to achieve 42 evaluable patients at the end of the study.
	Patients must satisfy the following eligibility criteria:
	Inclusion Criteria
	Patients must fulfil all of the following criteria in order to be included in the study:

1.	The patient has given written (personally signed and dated) informed consent before starting any study-related procedure, which means any assessment or evaluation that would not have formed part of their normal medical care.
2.	The patient is male and is 18 years of age or older.
3.	The patient has a histologically or cytologically confirmed diagnosis of prostate cancer and meets the following criteria:
	 Stage T3 or T4, N (any), M (any) (see Appendix 1) with a PSA >5ng/ml or
	 Biochemical relapse following radical prostatectomy or radical radiotherapy for prostate cancer
4.	Medical castration by means of LHRHa therapy is indicated for the patient.
5.	The patient has a life expectancy of at least 12 months.
6.	The patient is able and willing to comply with the requirements of the protocol.
Ex	clusion Criteria
	tients who fulfil any of the following criteria, will not be included in e study:
1.	The patient has undergone bilateral orchidectomy.

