4.2 Patient Withdrawal Criteria

If one or more of the following occurs, the patient will be withdrawn from the study:

- Patient decision to withdraw from the trial.
- Initiation of any oestrogen, any LHRHa (other than the Decapeptyl SR prescribed for this study) or any antiandrogen (other than the cyproterone acetate two week treatment as described in this protocol).
- Unacceptable safety or tolerability as determined by the Investigator.
- Concurrent, non-cancer related reason, which prevents regular follow up of the patient.
- General or specific changes in the patient's condition, which, in the Investigator's judgement, requires medical intervention and prohibits the patient from compliance with the protocol procedures.

If a patient discontinues from the study prematurely (i.e. prior to completion of the protocol), the primary reason for discontinuation will be determined and recorded. In all cases the Investigator will ensure that the patient receives medical follow-up as necessary.

Patients who withdraw from the study will not be replaced. Under no circumstances will patients be enrolled more than once.

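### The stated 84% power and cut-off of 39 belong to 42 evaluable patients, not to the all-treated population on which the primary test is run

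*Protocol*

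**What the plan says.** Section 8.3 (Sample Size Determination) tests a responder rate of at most 80% against one of at least 95%. It fixes 42 patients and a success count of 39, and gives the error rates and the expected loss together: "with an alpha-risk of 2% (one sided) and an 84% power. A drop out rate of up to 10% is anticipated". To allow for withdrawals, the number is then raised to at most 50 in section 8.3 and to 47 in the synopsis (Statistical Methods).

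The synopsis (Study Population) says what the 42 are: "Approximately 50 patients will be enrolled in order to achieve 42 evaluable patients at the end of the study". Evaluable is not among the populations defined in section 8.2.

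Section 8.2.1 states: "The primary analysis based on the primary efficacy endpoint(s) will be performed on the ITT population". Section 8.2 defines that population as "All treated subjects". Section 8.1 defines a drop-out as a treated subject who did not complete the study or the treatment, and section 4.2 says withdrawals are not replaced. Section 8.3.1 sets the primary test at one-sided 2.5%, and the synopsis names the exact binomial test at that level. The only success count given anywhere is 39.

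**The concern.** Inflating 42 to 47 or 50 protects the power only if patients who drop out are removed from the denominator, leaving about 42 to be tested. The stated primary population does the opposite, because every drop-out stays in it. The calculation and the analysis therefore use different denominators.

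Two things are at stake. First, a reader takes 84% as the chance that the primary test succeeds if the route works as hoped, and that figure is not derived for the test that will be run. Second, a success count of 39 has the intended error rate only when 42 patients are analysed. Carried over to 47 or 50 patients, it is a far weaker hurdle.

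**Working it through.** **Inputs.** Null rate 0.80, alternative 0.95, n = 42, cut-off 39, drop-out up to 10% (section 8.3); one-sided 2.5% (section 8.3.1); exact binomial test (synopsis); N = 47 (synopsis) or at most 50 (section 8.3); primary population all treated (sections 8.2 and 8.2.1).

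**Formula.** P(X ≥ r | n, p) is the upper binomial tail. The cut-off r at each N is the smallest count with P(X ≥ r | N, 0.80) ≤ 0.025.

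**The plan's own figures.** P(X ≥ 39 | 42, 0.80) = 0.0208 and P(X ≥ 39 | 42, 0.95) = 0.843, so the stated 2% and 84% are reproduced. 42 / 0.90 = 46.7, rounded up to 47, which reproduces the synopsis number.

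**Cut-off for the all-treated denominator.**
- N = 47: r = 44, with P(X ≥ 44 | 47, 0.80) = 0.0093.
- N = 50: r = 46, with P(X ≥ 46 | 50, 0.80) = 0.0185.
- If 39 were kept: P(X ≥ 39 | 47, 0.80) = 0.384 and P(X ≥ 39 | 50, 0.80) = 0.711.

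**Power under the readings that the protocol leaves open.**

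(a) 95% is the rate among all treated patients: power is P(X ≥ r | N, 0.95).

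(b) 95% is the rate among completers, and patients without a Month 4 serum total testosterone (STT) count as non-responders. With drop-out d, the all-treated rate is 0.95 × (1 − d): 0.931 at 2%, 0.9025 at 5% and 0.855 at 10%.

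(c) Drop-outs occur at random with probability 10% and are excluded. Power is the sum over m of P(m remain | N, 0.90) × P(X ≥ r(m) | m, 0.95), where r(m) is the exact cut-off for m patients.

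| Reading | N = 47 (cut-off 44) | N = 50 (cut-off 46) |
|---|---|---|
| (a) 95% among all treated | 79.3% | 89.6% |
| (b) 2% drop-out | 59% | 74% |
| (b) 5% drop-out | 32% | 45% |
| (b) 10% drop-out | 7.6% | 13.1% |
| (c) 10% drop-out, excluded (cut-off for the number remaining) | 80.6% | 82.3% |

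The two sizes are not bounds for the sizes between them, because the exact test moves in steps. Under (b) at 10% drop-out, N = 48 gives 15.6% and N = 49 gives 14.3%. Under (a), N = 48 gives 90.9%.

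Under (b), five patients without a Month 4 value make success impossible: 47 − 5 = 42 is below 44, and 50 − 5 = 45 is below 46.

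**The case against.** A reader might infer that the primary test has only about 8% to 13% power, so that a fully effective route would most likely be declared a failure. The protocol does not support that as a flat statement. It needs three things that the text does not fix.

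- **Every drop-out is a non-responder.** No section says so, and the scoring of a missing value is commonly left to a statistical analysis plan, which is not shown here. Section 8.1 counts a patient as a drop-out if he did not complete study or treatment, so some drop-outs could still have a Month 4 STT. Section 3.5.5 seeks an STT at early termination, without saying whether it serves the primary endpoint. Section 8.2.1 also allows exclusions from ITT at the data review meeting.
- **The 95% is the completer rate.** Section 8.3 attaches no such qualifier. Read with the ITT primary analysis, 95% may mean all treated patients, and power is then close to or above the stated 84%.
- **Drop-out is the full 10%.** The protocol gives this as an upper limit.

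It is also fair to say that a statistician applying the exact test at 2.5% would find the right cut-off for whatever N is analysed. The 38% and 71% error rates arise only if 39 is taken literally. Finally, 50 in the synopsis is the number enrolled, which section 8.1 defines as consented, so the number treated may be lower.

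All of this stands and makes the low power figures conditional. It does not remove the mismatch, because drop-outs are in the primary population by definition and the stated power and cut-off were computed without them.

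**Conclusion.** The misalignment is real and visible in the protocol alone. The 84% and the cut-off of 39 are exact for 42 patients and are not properties of the primary analysis on all treated patients. The correct cut-offs at the two stated sizes are 44 of 47 and 46 of 50.

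The size of the power problem depends on the reading. Power is about 79% to 91% over N = 47 to 50 if 95% is the all-treated rate, and about 81% to 82% at N = 47 and 50 if random drop-outs are excluded. If 95% is the completer rate and missing counts as failure, it falls to 32% or 45% at 5% drop-out, and to 7.6% or 13.1% at the ceiling. The last pair is the worst of these cases, not the expected one. This should be fixed, but the protocol does not show that the test is bound to fail.

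**What to change.** Keep ITT as the primary population. In section 8.3 and the synopsis:

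- give the cut-off for the number actually treated (44 of 47, 46 of 50) in place of a fixed 39;
- say whether the 95% refers to all treated patients or to completers;
- say how a treated patient without a Month 4 STT is scored;
- replace the single 84% by the power of that analysis at the anticipated drop-out.

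Report the analysis of patients with a Month 4 STT as a sensitivity analysis.

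Moving the primary analysis to an evaluable set, to rescue the 42-patient calculation, is not recommended. Section 4.2 withdraws patients for "Initiation of any oestrogen, any LHRHa (other than the Decapeptyl SR prescribed for this study) or any antiandrogen" (apart from the protocol's own two-week course). If poorly suppressed patients are among them, leaving them out could raise the observed rate. It would not preserve 84% either: with 10% random drop-out the power is 80.6% at N = 47 or 82.3% at N = 50.

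The cost is wording and a possibly less favourable power figure, with no extra patients.

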8.3.1 Significance Testing and Estimations

Statistical tests for the primary efficacy criterion will be performed one sided with a type I error rate set at 2.5%.

8.4 Statistical/Analytical Methods

Statistical analyses will be performed by staff from the Bristol Research and Development Support Unit. Statistical evaluation will be performed using SPSS and Stata.

8.4.1 Demographic and Other Baseline Characteristics

Descriptive summary statistics (n, mean, SD, median, minimum, maximum) or frequency counts of demographic and baseline data (medical history, concomitant disease pre-treatment AEs and on-going medical history, prior medications, baseline symptoms) will be presented for the ITT population.

8.4.2 Subject Disposition and Withdrawals

The numbers and percentages of subjects enrolled and included in the ITT/PP and safety populations will be tabulated by centre. The reasons for subject exclusions from each of the populations will also be tabulated. Primary reasons for discontinuation of study treatment will be tabulated.

8.4.3 *Efficacy Evaluation*

Primary Endpoint

The primary endpoint will be test the null hypothesis H0 that the proportion of responders (defined as subject who achieve STTCL (< 50 ng/dL) 4 months after

the first injection) is lower or equal to 80% against the alternative hypothesis H1 that the proportion of responders is larger or equal to 95%.

The secondary endpoints are:

- Proportion of subjects who achieve STTCL 1 month after the first injection.
- Proportion of subjects who achieve STTCL 1 month after the second injection.
- Changes in plasma triptorelin levels after administration of Decapeptyl SR by SC injection at all assessment time-points in comparison to Baseline.
- Changes in the levels of Serum Total Testosterone (STT) and Prostate Specific Antigen (PSA), after administration of Decapeptyl[®] SR by SC route injection at all assessment time-points in comparison to the Screening visit
- Changes in plasma triptorelin levels after administration of Decapeptyl SR at all assessment time-points from week 4.

Summary tables will be provided with the number and percentage of subjects with STTCL 1 month after the first and the second injection. Exact binomial 95% confidence intervals of proportions will also be provided. Descriptive statistics (N, Mean, SD, Median, Minimum and Maximum) as well as 95% confidence intervals will be calculated for STT / PSA / Plasma triptorelin levels at each timepoint and for changes from baseline and week 4 as relevant.

